For participants who are minors (i.e., 16-17-years-old), a waiver of parental consent has been requested, as described in Section 5.5.

Protections Against Emotional Discomfort: It is possible that participants may experience emotional discomfort in responding to assessments or session material. While every possible step will be taken to minimize such risk, consent documentation will make it clear that if participants have any concerns about any aspect of the study they may refuse to continue with the study at any time, without penalty. In addition, participants will be reminded during the course of their assessments that they can refuse to answer any questions and may discontinue participation at any time. Research staff and counselors at CSU will be thoroughly trained in appropriate responses to participant distress through trainings by a licensed clinical psychologist. This training will address the appropriate handling of imminent threats and provision of referrals to counseling services in less imminent clinical situations. Protocols have been developed by the research teams at CSU and Yale for mitigating such risks as employed in our other online and in-person treatment studies with YMSM.

HIV/STI testing might invoke some emotional discomfort. The CSU project coordinator, trained by PI, [name], and staff from Zuo An Cai Hong, all of whom have previous experience conducting at-home HIV/STI testing with YMSM, will seek HIV/STI testing consent from all participants during the video screen consent process, prior to study commencement.

HIV/STI counseling and testing will be led by study counselors, in consultation with Zuo An Cai Hong, which contributes an 11-year experience in HIV/STI testing and care and demonstrates high YMSM-sensitive testing expertise. Prior to study commencement, we will convene the counselors and review all protocols and reporting procedures (both to the Chinese epidemiological tracking system overseen and our study data system).

Confidentiality of results will be stressed during consent and contact with counselors, and on the at home HIV/STI kit instructions. A positive test is insufficient for diagnosis and participants will be directed to the nearby Zuo An Cai Hong clinic for treatment and follow up, unless the participant prefers to access care at health clinic of his choice. Counselors will urge participants to access testing at these sites beyond study-related testing. We will make every effort to ensure that participants with positive results are referred and have access to care with a Zuo An Cai Hong clinic for confirmatory testing and follow-up care. Zuo An Cai Hong will also report positive HIV/STI test results to the national reporting system for HIV and STIs.

Appropriate risk-reduction counseling will be provided to all participants at time of testing, as well as through the ESTEEM iCBT content they will receive. Enclosed within testing kits, all participants will receive lubricant and condoms. The rapid test results for both HIV and syphilis will be ready to be read by participants in 20 minutes. HIV/STI test results will be discussed with participants by study counselors during the same day as testing via WeChat. Like conventional HIV enzyme immunoassays (EIAs), rapid HIV/STI tests are screening (i.e., not diagnostic) tests that require diagnostic confirmation by Western Blots if reactive (positive). Participants who test preliminarily positive (or have inconclusive tests) will be immediately linked to Zuo An Cai Hong who would refer them to CDC for confirmatory testing, care, and treatment. Study counselors will offer to make an appointment for participants at a local Zuo An Cai Hong, which has 7 offices across Hunan province. Participants testing HIV positive will not be randomized into the study, as HIV negative status is one of the inclusion criteria, so they will receive immediate counseling by our counselors, followed by medical attention referred by Zuo An Cai Hong to which they will be promptly linked. Further, we will employ the same procedures as above to address potential distress upon realization of an HIV-positive status after the rapid test. See Section 6 of the protocol for further information in regard to procedures around the at home HIV/STI testing for the study.

Protections against breach of confidentiality: The likelihood that any additional breaches of confidentiality would occur is minimal, as steps will be taken to guard against this risk. All counselors and research staff will undergo rigorous training in maintaining participants' privacy and confidentiality and will be in possession of valid Collaborative Institutional Training Initiative (CITI) certificates or comparable trainings. Further, immediately upon providing consent, all participants will be assigned a unique study code number, which will only be kept on an electronic database that will be password-protected and located on a designated study computer at CSU that will not be connected to the Internet (i.e., offline). This information will not be stored with any other data and no other identifying information will appear on any form. All contact with participants will be made by counselors and research staff under explicit guidelines to preserve confidentiality when corresponding with participants. All materials with identifying information will be kept in one password-protected electronic file. Participants will provide alternative contact information (e.g., WeChat account

information) for compensation and study retention purposes. This information will be treated in the same confidential manner as all participant information, as described here.

Our iCBT platform employs numerous physical access controls (e.g., steel walls, keycard access system), systems access controls (e.g., login via two-factor authentication, encrypted passwords, required regular password changes), personal data access controls (e.g., privilege systems ensuring that study staff only can view information and edit settings that pertain to their role), data separation controls (e.g., study-specific database), data transfer access controls, intrusion and malware protection, audit logs, safety backups, and data erasure protocols. These protections ensure that participants' data will remain secure throughout the duration of the study and beyond. Additionally, no identifiable information will be stored on the iCBT platform at any point during the study.

Study data will be stored on either the secure Sojump survey platform, Karolinska Institutet's secure server, Yale's HIPAA-compliant Secure Box, and/or an offline computer in [name] lab at CSU. Session homework assignment data will be received at the Karolinska Institutet's server, which hosts the iCBT online platform for both study conditions (i.e., Chinese ESTEEM iCBT and self-monitoring). These session homework assignment data will also be downloaded to Yale's Secure Box drive upon retrieval from the Karolinska Institutet server, which will not include identifiable participant information; it will also remain on the Karolinska Institutet server after transfer to Yale. Participant session notes will be stored on Yale's Secure Box. One password-protected linking database containing participant names and ID codes will be kept on an offline computer in [name] lab at CSU and will only be accessible by CSU study staff via a separate password.

Participant tracking and scheduling data will be recorded on a study database stored on an offline computer in [name] lab at CSU. All study measures will be administered online via the secure Sojump survey platform. [name] and her team at CSU have used Sojump for several past studies. For data safety, [name] has a signed confidentiality contract with Sojump. Per the Sojump confidentiality contract, requisite technical measures will be implemented to ensure the security of our data stored on the Sojump server. Sojump is hosted in Allyun BGP room, data is stored in RAID (disk array), protected by enterprise-level firewall, and combined with daily backup to ensure the data security. Sojump supports multiple public level settings and password protection for questionnaires and results. Their staff is tightly regulated and restricted in their access to our data to ensure that our critical data will not be leaked." As part of this contract for this study, only one account login and password are provided to ensure confidentiality. Furthermore, each login requires a phone-based dual text authentication. All data from Sojump will be downloaded onto an offline computer. For weekly self-monitoring assessments and iCBT ESTEEM homework assignments conducted on the iCBT online platform, only participant IDs will be used; no participants' names or other identifying information will be used or stored on the iCBT online platform. For qualitative interviews, participant names will not be recorded and any identifying information will be removed from recordings prior to transcription. Interviews will be recorded on a secure offline device and transferred to an offline computer kept in [name] lab at CSU along with transcriptions.

Reporting requirements might be invoked in the case of participants reporting suicidality, homicidality, severe distress, or violence. Our lab's clinical protocol at Yale has successfully guided reporting of instances of suicidality, homicidality, severe emotional distress, violence, and child abuse/maltreatment in our other online-based RCTs (see IRB #2000025803). At CSU, a similar protocol has been adapted, and will be followed for participants reporting suicidality, homicidality, severe distress, violence, or child abuse/maltreatment. The protocol specifies that, in the event that a participant is at imminent risk of harming themselves or another person, as determined by a study staff member with mental health training, study

staff will contact local police (110) or paramedics (120). Only the minimal necessary identifying information will be provided to these personnel. In less imminent instances of distress, we will refer distressed participants to local mental or behavioral health services available in their area. All therapy homework will be reviewed every 24-48 hours by a clinical staff member trained in suicide assessment. Research and clinical staff members will receive an alert if the participant answers the online questionnaires in a manner that signals distress; such participants will be called by a clinical staff member to assess risk. Participants will be notified of the reporting requirements under these circumstances during the consent process. See the attached Clinical Protocol on IRES for detailed information regarding this clinical protocol.

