3.3 Objectives

The primary objective is to evaluate the preliminary efficacy of a Chinese-adapted version of iCBT ESTEEM on YMSM's sexual health and HIV risk behavior.

The secondary objectives of this study are to determine whether iCBT ESTEEM impacts HIV/STI results and symptoms of depression and anxiety, as well as whether baseline minority stress exposure moderates treatment efficacy, such that participants with the most minority stress exposure benefit more from iCBT ESTEEM than those in the self-monitoring

of stress and mood condition. An additional objective is to identify individual and institutional implementation barriers and facilitators of iCBT ESTEEM among Chinese YMSM.

4 Study Design

Aim 2 of the proposed prospective study will follow a 2-arm RCT design where 120 Chinese YMSM participants will be randomly assigned to one of two conditions:

- 1) ESTEEM iCBT: This online CBT treatment consists of 10 weekly modules that participants will complete over the course of 10 weeks. Modules contain weekly psychoeducational text and vignettes about minority stress and mental health; brief videos illustrating the CBT skills; and homework exercises that therapists review and provide feedback on. Homework exercises include weekly tracking of stressful situations and mood, practicing new skills (e.g., mindfulness, cognitive restructuring), and exercises related to considering the origins of stress and negative emotions that participants may be experiencing. Therapists provide feedback after each homework assignment, including reviewing each participant's treatment goals as part of the first session's homework. Therapists who support this condition will be instructed to incorporate SGM-specific content and feedback into homework reviews. Therapists will be mental health counselors in [name] lab at CSU who possess an advanced degree in a mental health field with significant prior experience treating Chinese YMSM with sexual and mental health concerns. In the US, modules were adapted directly from the in-person materials (e.g., therapist manual, participant handouts) used in our previously successful trials of this treatment. The treatment has also been recently, culturally adapted for in-person treatment among Chinese YMSM and found to be acceptable and feasible.

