- 2) Self-monitoring control: In this control condition, participants will be asked to indicate their past 7-day mood, stress experiences, and mental and behavioral health on an online survey. This type of self-monitoring has been shown to yield improvement in behavioral health outcomes. Self-reporting SGM stress experiences has also been shown to produce reductions in depression symptoms over time. Participants will record these experiences once per week for 10 weeks.

[figure not shown]
Prior to randomization, participants will complete an online screener, video screener on WeChat, at-home HIV/STI testing kit for HIV and syphilis, and consent call on WeChat (see Section 6.1 Study Procedures for more information about these steps of the study). For the at-home HIV/STI testing kit for HIV and syphilis, rapid test results will be ready to be read by participants in 20 minutes. HIV/STI test results will be discussed with participants by study counselors during the same day as testing via WeChat. A CSU research team member will contact participants on WeChat after 5 business days of sending the HIV/STI testing kit if the participant has not sent the CSU team a photo of their results. Specific procedures regarding risks for the at-home HIV/STI testing is outlined in Section 2.2.

To assess intervention efficacy, participants will be assessed at three time-points: baseline, immediately post-treatment (4-month follow-up), and 8-month follow-up. Participants will complete validated measures online of past-30-day HIV-risk behavior (e.g., condomless anal sex), mental health (e.g., depression, anxiety), and minority stressors (e.g., discrimination) at all three times points. At 8-month follow-up, participants will be mailed and asked to complete the same at-home HIV/STI testing kit for HIB and syphilis described above.

After completing the baseline assessment, participants randomized to ESTEEM iCBT will be assigned a study therapist and will be contacted by their therapist to schedule a 30-minute

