For participants assigned to ESTEEM iCBT, they will be assigned a study therapist and will be contacted by their therapist to schedule a 30-minute introductory call via WeChat. During this conversation, therapists will explain the structure of the study and briefly discuss the participant's motivations and goals for participating in the study. All participants will then complete one session (i.e., ESTEEM iCBT or self-monitoring) per week. If participants miss

a session, as determined by daily therapist and RA review of session access and self-monitoring or homework completion, they will receive a reminder via a WeChat message to complete the session. Participants will also be asked to schedule a check-in WeChat call with their study therapist two-weeks post-randomization to discuss their progress through the study sessions. Participants will have a window period of four months (i.e., 17 weeks) to complete all 10 sessions.

Lastly, all participants will be sent messages on WeChat to complete 4-month and 8-month follow-up assessments. For all assessment time points, automatically generated alerts from Sojump will be sent to CSU study staff in response to any participants who indicate suicidality in response to suicidality assessments, at which point a clinical staff member part of the CSU team will implement the clinical protocol. For the 8-month follow-up, a second at-home HIV/STI testing kit will be mailed to participants. The same procedure as described above will be followed in regard to participants administering this test and reporting results to CSU study counselors for follow-up.

See Table 1 in Section 11.1 for a Visit Schedule Table with study procedures listing all points of data collection.

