7.2.3 Interim Analysis (if applicable)

The DSMB will review all risk-related data (e.g., HIV risk behavior, suicidality, and depression) by condition during each annual meeting. The DSMB will decide whether to review this information while masked to condition assignment.

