9.5 Study Discontinuation

The research team will discuss discontinuation of the study in the event that participants in either condition experience unanticipated adverse events (e.g., increased active suicidality) over the course of study completion. The DSMB and IRB will be involved in such a discussion.

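### Suicidality is ascertained more intensively in the iCBT arm during treatment, and Protocol 7.2.3 does not separate comparable from non-comparable data in the DSMB's review by condition

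*Protocol*

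**What the plan says.** **Channels described for iCBT only.** Protocol 2.2: "All therapy homework will be reviewed every 24-48 hours by a clinical staff member trained in suicide assessment". Section 4 lists "homework exercises that therapists review and provide feedback on" under ESTEEM iCBT and not under the control. Section 8.5 likewise attributes homework to iCBT participants and weekly surveys to everyone. Section 6.1 adds: "For participants assigned to ESTEEM iCBT, they will be assigned a study therapist and will be contacted by their therapist", for a 30-minute introductory call.

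**Control content.** In Section 4, "participants will be asked to indicate their past 7-day mood, stress experiences, and mental and behavioral health on an online survey", once a week for 10 weeks.

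**Channels covering both arms.** Section 2.2 continues: "Research and clinical staff members will receive an alert if the participant answers the online questionnaires in a manner that signals distress", after which a clinical staff member calls to assess risk. Section 5.5 has the clinical team review every participant's survey responses, as well as therapy exercises, for suicidality, with contact inside one business day where distress is indicated. Section 6.1: "For all assessment time points, automatically generated alerts from Sojump will be sent to CSU study staff in response to any participants who indicate suicidality". Section 4.2.2 gives SIDAS (past-month recall) at baseline, 4 and 8 months.

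**Use of the data.** Section 7.2.3: "The DSMB will review all risk-related data (e.g., HIV risk behavior, suicidality, and depression) by condition". Section 8.7 also sends adverse event reports to the DSMB. Section 9.5 has the team discuss discontinuation if "participants in either condition experience unanticipated adverse events (e.g., increased active suicidality) over the course of study completion". SAP 7.2 describes how events are reported, but not how they are elicited.

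**The concern.** The two arms offer different opportunities to notice suicidality while treatment runs. A man in the iCBT arm writes exercises that suicide-trained staff read within a day or two, and a therapist responds to him. A control fills in three weekly questionnaires (depression severity, anxiety severity, minority stress), none described as a suicidality measure, on a platform other than the one that Section 6.1 names for the automatic suicidality alerts.

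If events found through homework or therapists are tallied by arm beside events found through common questionnaires, the tally mixes occurrence with opportunity to observe. An excess in iCBT could be read as harm when it reflects closer watching. Equal counts could hide a true benefit of iCBT, or missed events in controls. Expected counts are small, so one or two extra detections could colour the DSMB's reading or the final safety table.

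**Working it through.** The documents give no figure for suicidality detection, so there is nothing to reproduce. The check has three parts.

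**1. Channels by arm after randomization**

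| Channel (Protocol section) | iCBT | Control | Period |
|---|---|---|---|
| Homework review every 24-48 h (2.2, 4) | yes | no | treatment window, up to 17 weeks |
| Assigned therapist, feedback, introductory call (4, 6.1) | yes | no | treatment window |
| Two-week check-in call (6.1) | yes | unclear | week 2 |
| Weekly surveys (4.2.2), responses reviewed (5.5) | yes | yes | 10 weeks |
| Questionnaire distress alert, then clinical call (2.2) | yes | yes | not limited by arm or period |
| SIDAS with Sojump alerts (4.2.2, 6.1) | yes | yes | 4 and 8 months |

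Every control channel also exists in iCBT; the reverse is not true. After the treatment window the arms are alike.

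**2. Scheduled looks and coverage**

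- Common to both arms: 10 weekly surveys + 2 follow-up assessments = 12.
- Extra in iCBT: 10 homework reviews + introductory call + two-week call = 12.
- Totals: 24 against 12. If the two-week call also goes to controls, 24 against 13.
- SIDAS alone: 2 against 2.
- Taking month 8 as about 243 days, homework review spans 70/243 = 29% to 119/243 = 49% of follow-up in iCBT (10 to 17 weeks). Two SIDAS windows of 30 days cover 60/243 = 25% in both arms.

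These figures describe schedules. They are not detection probabilities.

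**3. Illustration under assumed detection**

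Expected detected cases = n × true rate × detection probability, with n = 60 per arm. With equal true rates, the apparent ratio is the ratio of the two detection probabilities. All rates and probabilities here are assumptions.

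- Detection 60-80% in iCBT and 25-40% in control: the ratio runs from 0.60/0.40 = 1.5 to 0.80/0.25 = 3.2.
- At a 5% true rate: iCBT 60 × 0.05 × (0.60 to 0.80) = 1.8 to 2.4 cases; control 60 × 0.05 × (0.25 to 0.40) = 0.75 to 1.2.
- At a 10% true rate: iCBT 3.6 to 4.8; control 1.5 to 2.4.

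A second set assumes 90% in iCBT against 70%, 50% or 30% in control. The chance that detection alone gives p < .05 uses the normal approximation Φ[(|p1 − p2| − 1.96·se0)/se1], with p1 and p2 the detected proportions and se0 and se1 the pooled and unpooled standard errors.

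| Control detection | Ratio | Cases at 10% true rate | Chance of p < .05 at 10% | at 5% | at 20% |
|---|---|---|---|---|---|
| 70% | 1.29 | 5.4 vs 4.2 | 6% | 5% | 9% |
| 50% | 1.8 | 5.4 vs 3.0 | 14% | 9% | 24% |
| 30% | 3.0 | 5.4 vs 1.8 | 28% | 16% | 53% |

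For the 30% row at a 10% true rate: p1 = 0.09, p2 = 0.03, se0 = √(0.06 × 0.94 × 2/60) = 0.0434, se1 = √[(0.09 × 0.91 + 0.03 × 0.97)/60] = 0.0430, so Φ[(0.06 − 0.0850)/0.0430] = Φ(−0.58) = 0.28. The approximation is rough at counts this small. With equal detection the ratio is 1.0.

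**The case against.** The strongest reply is that the DSMB comparison may already be a like-for-like one. Section 7.2.3 names suicidality beside HIV risk behavior and depression, both study outcomes, and the SAP's suicidality outcome is SIDAS, given on one schedule to both arms. This is a fair reading, but it does not close the point. The phrase in 7.2.3 covers all risk-related data, adverse event reports also reach the DSMB under 8.7, and 9.5 speaks of active suicidality, which Section 5.3 defines as intent or a plan. That is not plainly a questionnaire score.

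The reply is right on several other matters, and a reader should not go further than the text allows:

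- A reader might infer that suicidality is sought in the iCBT arm only, and only during treatment. That is true of homework review, not of detection as a whole. The alerts, the survey review and the 8-month assessment in the table cover controls too. Section 6.1 also has staff check weekly completion daily and send reminders in both arms, and the weekly minority stress form has one open-ended item for everyone.
- A reader might infer that any difference by condition is suspect. SIDAS differences do not depend on the extra iCBT channels.
- A reader might infer that the iCBT count must fall once treatment ends. Only the part found through homework and therapists would, and no section defines such a count.
- A reader might take a two- to three-fold inflation as established. The ratio only restates the assumed detection rates.

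The Clinical Protocol that Section 2.2 refers to is not among the documents. It may set a review interval for the weekly surveys, which would narrow the gap. It could not give controls homework or a therapist.

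**Conclusion.** The point holds as one of unequal intensity. During a window of up to 17 weeks, iCBT has every detection channel that controls have, plus homework review, therapist feedback and the introductory call. Section 7.2.3 does not say which suicidality data are compared by condition, so staff-detected events may enter a between-arm reading that they cannot support. Masking the DSMB, which 7.2.3 leaves optional, would not help, because the counts would still differ.

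The size is unknown. The ratios of 1.5 to 3.2, and 1.29 to 3.0 under the second set, rest wholly on assumed detection rates, and the gap is a few cases per arm at most for true rates of 5-10%. The conclusion assumes that homework is confined to iCBT, as Sections 4 and 8.5 indicate. It does not depend on which arm receives the two-week call. This is a low-cost improvement to safety reporting, with no bearing on the primary analysis.

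**What to change.** In Protocol 7.2.3 and the SAP safety section (7.2), state that the between-arm comparison of suicidality rests on measures taken on the same schedule in both arms: SIDAS at baseline, 4 and 8 months, with PHQ-9 as support.

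Continue to show the DSMB, and report in the final safety tables, all other suicidality events by arm and by source of detection: homework, therapist contact, weekly survey, assessment alert. Label these as not comparable between arms. Nothing is withheld from the DSMB. Clinical handling of individual participants and the discontinuation trigger in 9.5 stay unchanged.

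The cost is one added field for source of detection and a sentence in each document. The SAP (revised 1.24.23) describes DSMB meetings in the past tense, so the change may now matter mainly for final reporting; the source of earlier events could be sought in the homework data and session notes that Section 2.2 says are stored. The downside is that comparable data exist at only two post-baseline visits, each recalling about one month.
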